16.1 Appendix 1: Clinically notable laboratory values and vital signs

Refer to [Appendix 1.1](#) for clinically notable vital sign values for adolescents.

Refer to [Appendix 2](#) for clinically notable laboratory values for hepatotoxicity.

Refer to [Appendix 3](#) for clinically notable laboratory values for nephrotoxicity.

The following other specific criteria have been identified for this study:

Platelets < 75 000/ μ L

- Any patient who have platelets < 75 000/ μ L after being randomized should discontinue study treatment.

For all other laboratory assessments, the Central Laboratory will flag laboratory values falling outside of the normal ranges on the Central Laboratory Report (which the investigator should review and sign-off) and the investigator will report any values considered clinically significant in the CRF as an AE.

Notable values for vital signs and change from baseline will be summarized.

Notable values for adults are defined as follows:

- heart rate of < 60 and > 100 bpm
- systolic blood pressure of < 90 and \geq 140 mmHg
- diastolic blood pressure of < 60 and \geq 90 mmHg

For ECGs a notable QTc value is defined as a QTcF interval of greater than 450 ms for males or greater than 460 ms for females – all such ECGs will be flagged by the Central CRO’s cardiologist and require assessment for clinical relevance by the investigator. For adolescent subjects, the Central CRO will use age-and gender-specific reference values.

16.1.1 Appendix 1.1: Clinically notable vital signs – adolescent subjects

16.1.1.1 Guideline for pediatric blood pressure measurements:

Table 16-1 Best Blood Pressure (BP) Measurement Practices - Pediatrics

 1. The child should be seated in a quiet room for 3–5 min before measurement, with the back supported and feet uncrossed on the floor. 2. BP should be measured in the right arm for consistency, for comparison with standard tables, and to avoid a falsely low reading from the left arm in the case of coarctation of the aorta. The arm should be at heart level, supported, and uncovered above the cuff. The patient and observer should not speak while the measurement is being taken. 3. The correct cuff size should be used. The bladder length should be 80%–100% of the circumference of the arm, and the width should be at least 40%. 4. For an auscultatory BP, the bell of the stethoscope should be placed over the brachial artery in the antecubital fossa, and the lower end of the cuff should be 2–3 cm above the antecubital fossa. The cuff should be inflated to 20–30 mm Hg above the point at which the radial pulse disappears. Overinflation should be avoided. The cuff should be deflated at a rate of 2–3 mm Hg per second. The first (phase I Korotkoff) and last (phase V Korotkoff) audible sounds should be taken as systolic blood pressure and diastolic blood pressure. If the Korotkoff sounds are heard to 0 mm Hg, the point at which the sound is muffled (phase IV Korotkoff) should be taken as the diastolic BP, or the measurement repeated with less pressure applied over the brachial artery. The measurement should be read to the nearest 2 mm Hg. 5. To measure BP in the legs, the patient should be in the prone position, if possible. An appropriately sized cuff should be placed midhigh and the stethoscope placed over the popliteal artery. The systolic BP in the legs is usually 10%–20% higher than the brachial artery pressure. 
Adapted from Pickering TG et al 2005

--

Table 16-2 Upper and lower limits for adolescents’ vital signs that may be considered of concern if newly identified may be identified using the following table for guidance¹

Age	Systolic BP ^{2,3}	Diastolic BP ^{2,3}	HR ³
12 yrs	101-135	59-91	60-110
13 yrs	104-137	60-91	60-110

Age	Systolic BP ^{2,3}	Diastolic BP ^{2,3}	HR ³
14 yrs	106-140	60-92	60-110
15 yrs	107-142	61-93	60-110
16 yrs	108-145	63-94	60-110
17 yrs	108-147	64-97	60-100
18 yrs	-	-	60-100

¹ The table above was developed from multiple resources listed below. The normal values for vital signs in children vary greatly with age, growth and development. The purpose of these values is to guide investigators to identify or screen for values of concern in pediatric patients by age. These are not normal values, which can be found in sources such as the Harriet Lane Pediatric Handbook but rather are upper and lower limits for children's vital signs that may be considered of concern if newly identified. The significance of these findings must be considered in view of the patient's disease, time course and overall clinical condition.

² Based on percentiles by height (50th - 99th)

³ (Arcara K and Tschudy M 2011). The Harriet Lane Handbook
[who.int/childgrowth/standards/w_f_a_tables_p_girls/en/index.html](http://www.int/childgrowth/standards/w_f_a_tables_p_girls/en/index.html)
[who.int/childgrowth/standards/second_set/hcfa_girls_p_exp.txt](http://www.int/childgrowth/standards/second_set/hcfa_girls_p_exp.txt)
[who.int/childgrowth/standards/second_set/hcfa_boys_p_exp.txt](http://www.int/childgrowth/standards/second_set/hcfa_boys_p_exp.txt)

16.2 Appendix 2: Liver event and laboratory trigger definitions and follow-up requirements

Table 16-3 Liver event and laboratory trigger definitions

	Definition/ threshold
LIVER LABORATORY TRIGGERS if ALT, AST and TBL normal at baseline	
 ALT or AST >5 × ULN ALP > 2 × ULN (in the absence of known bone pathology) TBL > 3 × ULN (in the absence of known Gilbert syndrome) ALT or AST > 3 × ULN and (TBL > 2 x ULN or INR > 1.5) 
 Potential Hy's Law cases defined as ALT or AST > 3 x ULN, combined with elevation of serum TBL to > 2 x ULN (mainly conjugated fraction), without notable increase of ALP to > 2 ULN Any clinical event of jaundice (or equivalent term) ALT or AST > 3 × ULN accompanied by (general) malaise, fatigue, abdominal pain, nausea, or vomiting, or rash with eosinophilia Any adverse event potentially indicative of a liver toxicity
If ALT or AST abnormal at baseline:	
 ALT or AST > 3 x baseline or > 300 U/L (whichever occurs first)

Table 16-4 Follow-up requirements for liver laboratory triggers – ALT, TBL with and without liver symptoms

ALT	TBL	Liver Symptoms	Actions
ALT increase without bilirubin increase:			
If normal at baseline: ALT > 3 × ULN If elevated at baseline: ALT > 2 × baseline or > 300 U/L (whichever	Normal For patients with Gilbert's syndrome: No change in	None	
 No change to study treatment Measure ALT, AST, ALP, GGT,

ALT	TBL	Liver Symptoms	Actions
occurs first)	baseline TBL		TBL, INR, albumin, CK, and GLDH in 48-72 hours. 
 Follow-up for symptoms.
If normal at baseline: ALT > 5 × ULN for more than two weeks If elevated at baseline: ALT > 3 × baseline or > 300 U/L (whichever occurs first) for more than two weeks	Normal For patients with Gilbert's syndrome: No change in baseline TBL	None	
 Interrupt study drug Measure ALT, AST, ALP, GGT, TBL, INR, albumin, CK, and GLDH in 48-72 hours. Follow-up for symptoms. Initiate close monitoring and workup for competing etiologies. Study drug can be restarted only if another etiology is identified and liver enzymes return to baseline.
If normal at baseline: ALT > 8 × ULN	Normal	None	
ALT increase with bilirubin increase:			
If normal at baseline: ALT > 3 × ULN If elevated at baseline: ALT > 2 × baseline or > 300 U/L (whichever occurs first)	TBL > 2 x ULN (or INR > 1.5) For patients with Gilbert's syndrome: Doubling of direct bilirubin	None	
If normal at baseline: ALT > 3 × ULN If elevated at baseline: ALT > 2 × baseline or > 300 U/L (whichever occurs first)	Normal or elevated	Severe fatigue, nausea, vomiting, right upper quadrant pain	

Table 16-5 Follow-up requirements for liver laboratory triggers – isolated hyperbilirubinemia

Criteria	Actions required	Follow-up monitoring
TBL (isolated)		
>1.5 – 3 × ULN	Maintain treatment Repeat LFTs within 48-72 hours	Monitor LFTs weekly until resolution to ≤ Grade 1 or baseline
> 3 - 10 × ULN (in the absence of known Gilbert syndrome)	Interrupt treatment Repeat LFT within 48-72 hours Hospitalize if clinically appropriate Establish causality Record the AE and contributing factors (eg, conmeds, med hx, lab) in the appropriate CRF	Monitor ALT, AST, TBL, Alb, PT/INR, ALP and GGT weekly until resolution to ≤ Grade 1 or baseline Test for hemolysis (eg, reticulocytes, haptoglobin, unconjugated [indirect] bilirubin)
> 10 × ULN	Discontinue the study treatment immediately Hospitalize the patient Establish causality Record the AE and contributing factors (eg, conmeds, med hx, lab) in the appropriate CRF	ALT, AST, TBL, Alb, PT/INR, ALP and GGT until resolution (frequency at investigator discretion)

Any AE potentially indicative of a liver toxicity	Consider study treatment interruption or discontinuation Hospitalization if clinically appropriate Establish causality Record the AE and contributing factors (eg, conmeds, med hx, lab) in the appropriate CRF	Investigator discretion
---	--	-------------------------

Based on investigator’s discretion investigation(s) for contributing factors for the liver event can include: serology tests, imaging and pathology assessments, hepatologist’s consultancy; obtaining more detailed history of symptoms and prior or concurrent diseases, history of concomitant drug use, exclusion of underlying liver disease.

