10.2 Additional Safety Monitoring

10.2.1 Liver safety monitoring

To ensure subject safety and enhance reliability in determining the hepatotoxic potential of an investigational drug, a standardized process for identification, monitoring and evaluation of liver events must be followed.

The following two categories of abnormalities / AEs have to be considered during the course of the study (irrespective of whether classified/reported as AE/SAE):

[figure not shown]
- Liver laboratory triggers, which will require repeated assessments of the abnormal laboratory parameter
- Liver events, which will require close observation, follow-up monitoring and contributing factors are recorded on the appropriate CRFs

Please refer to [Table 16-3](#) in [Appendix 2](#) for complete definitions of liver laboratory triggers.

Once a subject is exposed to study treatment, every liver event defined in [Table 16-3](#) should be followed up by the investigator or designated personnel at the trial site, as summarized below. Additional details on actions required in case of liver events are outlined in [Table 16-4](#) and [Table 16-5](#). Repeat liver chemistry tests (ALT, AST, TBL, prothrombin time (PT)/INR, ALP and GGT) to confirm elevation.

- These liver chemistry repeats will be performed using the central laboratory. If results will not be available from the central laboratory, then the repeats can also be performed at a local laboratory to monitor the safety of the subject. If a liver event is subsequently reported, any local liver chemistry tests previously conducted that are associated with this event should have results recorded on the appropriate CRF.
- If the initial elevation is confirmed, close observation of the subject will be initiated, including consideration of
 - Treatment interruption if deemed appropriate
 - Discontinuation of the investigational drug (refer to [Section 9.1.1](#)), if appropriate
 - Hospitalization of the subject if appropriate
 - Causality assessment of the liver event

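### Both combined liver triggers count ALT or AST, but the matching action rows name ALT only, so AST-led cases with TBL > 2 to 3 x ULN, INR > 1.5 or a shared symptom have no laboratory-threshold rule for interruption or restart

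*Protocol*

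**What the plan says.** Protocol Section 16.2, Table 16-3, has two triggers that combine a transaminase rise with a second finding, and both accept either enzyme. The first is "ALT or AST > 3 × ULN and (TBL > 2 x ULN or INR > 1.5". Potential Hy's Law is its bilirubin sub-case, "cases defined as ALT or AST > 3 x ULN, combined with elevation of serum TBL to > 2 x ULN", further limited to mainly conjugated bilirubin without a notable ALP rise. The second is the same transaminase limit "accompanied by (general) malaise, fatigue, abdominal pain, nausea, or vomiting, or rash with eosinophilia".

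Section 10.2.1 says that every Table 16-3 event should be followed up: "Additional details on actions required in case of liver events are outlined in" Tables 16-4 and 16-5. It also asks for a first step: "Repeat liver chemistry tests (ALT, AST, TBL, prothrombin time (PT)/INR, ALP and GGT) to confirm elevation".

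Table 16-4 is titled for "ALT, TBL with and without liver symptoms", and its five criteria rows all set ALT thresholds. One pairs ALT with TBL > 2 x ULN or INR > 1.5. Another pairs ALT with "Severe fatigue, nausea, vomiting, right upper quadrant pain". The instruction to interrupt and the restart rule, "Study drug can be restarted only if another etiology is identified and liver enzymes return to baseline", stand only in this table. Table 16-5 covers isolated hyperbilirubinemia and has one further row for any adverse event that may indicate liver toxicity.

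**The concern.** The trigger table and the action table disagree on which enzyme counts. An AST-led case can meet a combined trigger, even the potential Hy's Law definition, and then meet no row of the table that carries the interruption and restart rules. Whether the next four-weekly dose is held, and what must be seen before dosing resumes, then rests on judgement and not on a written threshold.

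A written rule has some practical value here. Under Section 6.7.2, self-administering subjects hold three or four kits and attend clinic every 12 to 16 weeks, so holding a dose needs an active instruction. CK, which helps tell a muscle source of AST from a liver source, is also not required by rule in these cases.

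**Working it through.** No arithmetic model applies. The check maps each trigger to its action row, using the normal-baseline thresholds.

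**Enzyme named**

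| Second finding | Table 16-3 trigger | Matching Table 16-4 row |
|---|---|---|
| TBL > 2 x ULN or INR > 1.5 | ALT or AST | ALT |
| Symptoms | ALT or AST | ALT |

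AST is named in 2 of 2 triggers and 0 of 2 matching rows. The other three Table 16-4 criteria rows (ALT > 3 x ULN; > 5 x ULN for more than two weeks; > 8 x ULN) do not name it either, so the count for the whole table is 0 of 5. AST appears there only as a test to re-measure.

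**Action cells.** In the extracted text the cells of the two combined rows are blank. They are read as one merged cell carrying the instruction to interrupt. If they were truly empty, ALT-led cases would also lack an action, and adding AST would change nothing.

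**Test case: AST > 3 x ULN, ALT not > 3 x ULN**

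| Second finding | Table 16-4 row met | Table 16-5 laboratory row |
|---|---|---|
| TBL > 2 to 3 x ULN | none | isolated-TBL row, if it applies at all: keep treating |
| INR > 1.5 | none | none |
| Symptom on both lists | none | none |
| TBL > 3 to 10 x ULN | none | interrupt, if *isolated* means without ALT increase; no restart condition |
| TBL > 10 x ULN | none | discontinue, on the same reading |

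If ALT also exceeds 3 x ULN, a Table 16-4 row is met and there is no gap.

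**Symptoms.** Table 16-3 lists six and Table 16-4 lists four. Two match (nausea, vomiting). Two are narrower in Table 16-4 (fatigue only if severe, abdominal pain only in the right upper quadrant). Two are absent (malaise, rash with eosinophilia). The absent two are missing whichever enzyme leads, so they are not part of the ALT/AST contrast.

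**Work-up.** Table 16-4 lists nine tests: ALT, AST, ALP, GGT, TBL, INR, albumin, CK and GLDH. The Section 10.2.1 repeat panel has six of them. The difference is 9 − 6 = 3: albumin, CK and GLDH.

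**Other provisions checked**

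- Section 10.2.1: once a rise is confirmed, close observation starts, with causality assessment and follow-up; interruption is left to judgement.
- Table 16-5 adverse-event row: interruption or discontinuation is to be considered.
- Section 9.1.1: its liver item points back to Appendix 2; its general item makes stopping mandatory where continuing might put the subject at risk.
- Section 6.5.1: any interruption is discussed with the sponsor; no biochemical criterion.

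None supplies an AST threshold or a restart condition.

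**The case against.** A reader might infer that an AST-led case has no action at all. The documents do not support that. Section 10.2.1 applies to AST triggers as well, so repeat tests and close observation follow. Section 10.1.1 treats a clinically significant abnormal laboratory value as an adverse event, so such a case would ordinarily reach the adverse-event row of Table 16-5. The general stop in Section 9.1.1 has a low bar and would probably catch many true cases. What is missing is a mandatory threshold row, not every response.

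A reader might also infer that the gap covers every TBL above 2 x ULN. That holds only if *isolated* is read strictly. TBL > 3 x ULN is a trigger in its own right in Table 16-3. The word is not defined, and since Table 16-4 is organised by ALT it can be taken to mean without ALT increase. Equally, the keep-treating row at > 1.5 to 3 x ULN should not be read as an instruction to go on dosing a potential Hy's Law case, because its heading limits it to isolated TBL.

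An ALT-led action table could be a deliberate choice: broad triggers, then mandatory action on the more liver-specific enzyme. The protocol does not say so. SAP Section 5.4, Table 5-11, counts ALT- or AST-led cases as potential Hy's Law, so the report would count cases for which the action table has no row. The trigger at > 5 x ULN has the same mismatch, but Table 16-4 itself treats a transaminase rise alone more leniently, so leaving those rows on ALT is easier to defend.

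The consequence is small. Entry excludes AST, ALT or TBL above 1.5 x ULN at Visit 1 or 2, and the study has been terminated (SAP Section 1.2). Both points stand, and they limit the weight of the finding.

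**Conclusion.** The point holds within these limits. For AST > 3 x ULN with ALT not > 3 x ULN, together with TBL > 2 to 3 x ULN, INR > 1.5 or a symptom on both lists, no laboratory-threshold row requires interruption, sets the restart condition or requires CK and GLDH. Above TBL 3 x ULN the gap exists only on the strict reading of *isolated*. On the looser reading, interruption or discontinuation is covered, but the interruption row still gives no restart condition.

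The harm and the remedy both assume that the blank Table 16-4 cells are merged under the instruction to interrupt, which is the likely layout. The documents give no frequency for such cases; the entry limits suggest that they are rare. No endpoint, analysis or safety count changes. This is a low-cost correction to a safety rule and should be made, but it does not threaten the trial's conclusions.

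**What to change.** In Table 16-4, write ALT or AST in the two rows for a rise with TBL/INR and a rise with liver symptoms, for both normal and elevated baseline, keeping the existing multiples. State at Table 16-5 whether the isolated-TBL rows apply when a transaminase trigger is met. Aligning the two symptom lists at the same time is optional.

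The cost is wording in two rows and one note, by protocol amendment. AST, ALT and TBL are already in the routine chemistry panel, and INR is in the Section 10.2.1 repeat panel. The downside is a few extra interruptions and work-ups for AST rises of non-hepatic origin, which the CK already in the Table 16-4 work-up helps identify. Because this study was terminated, an amendment matters here only while subjects are still being dosed. The amendment log says that Table 16-4 came from the sponsor's protocol template, so the correction is also worth making there.

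### Table 16-3 ties its combined and symptom liver triggers to normal baseline values, so some raised-baseline ALT cases have an action but no declared trigger, and raised-baseline AST has no numeric combined threshold

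*Protocol*

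**What the plan says.** Protocol Section 10.2.1 sends sites to Table 16-3 "for complete definitions of liver laboratory triggers". It then says that every liver event defined there "should be followed up by the investigator or designated personnel at the trial site, as summarized below", and points to Tables 16-4 and 16-5 for further detail on actions.

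Table 16-3 (Appendix 2) has two rows.

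- The first is headed "LIVER LABORATORY TRIGGERS if ALT, AST and TBL normal at baseline". It holds the combined trigger, "ALT or AST > 3 × ULN and (TBL > 2 x ULN or INR > 1.5", with the potential Hy's Law definition beneath it. It also holds the trigger for ALT or AST above 3 × ULN with symptoms, and the triggers for TBL above 3 × ULN and ALP above 2 × ULN.
- The second, for abnormal baseline ALT or AST, holds one line: "ALT or AST > 3 x baseline or > 300 U/L (whichever occurs first".

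Table 16-4 is titled "Follow-up requirements for liver laboratory triggers – ALT, TBL with and without liver symptoms". Its combined and symptomatic lines use, for raised baselines, "If elevated at baseline: ALT > 2 × baseline or > 300 U/L (whichever occurs first". The combined line pairs this with "TBL > 2 x ULN (or INR > 1.5"; the other line pairs it with liver symptoms. Its thresholds are for ALT only, and AST appears only among the tests to repeat.

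Table 16-5 covers isolated TBL elevation without a baseline condition. Its last row covers any AE that may indicate liver toxicity, with follow-up at the investigator's discretion.

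Exclusion criterion 20 (Section 5.2) excludes ALT, AST or TBL only above 1.5 × ULN at Visit 1 or Visit 2. SAP Table 5-11 (Section 5.4) counts ALT or AST above 3 × ULN with TBL above 2 × ULN and ALP below 2 × ULN as potential Hy's Law, with no baseline condition.

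**The concern.** Eligible subjects can start with mildly raised ALT, AST or TBL. For them, the table that declares triggers and the tables that prescribe actions do not line up.

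For normal baselines the combined and symptom thresholds agree across Tables 16-3 and 16-4, at above 3 × ULN in both. The isolated raised-baseline tier also agrees, at 3 × baseline or 300 U/L, although Table 16-4 adds a duration. Only the raised-baseline combined and symptom tiers lack a counterpart in Table 16-3. That looks more like an alignment slip than deliberate tiering.

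A site that declares triggers strictly from Table 16-3 would not start the Section 10.2.1 steps for a result on which Table 16-4 requires action. Rising transaminases with rising bilirubin or INR is the pattern that a liver monitoring plan most needs to catch consistently.

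**Working it through.** The plan states no figure to reproduce. The check sets the rules side by side. Let b be the baseline in multiples of ULN.

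**Raised baseline ALT, with TBL > 2 × ULN, INR > 1.5 or symptoms.** Table 16-4 acts above 2b × ULN and Table 16-3 triggers above 3b × ULN. Both also fire above 300 U/L. That limit narrows the gap only if ULN > 300/(3b), and closes it only if ULN ≥ 300/(2b).

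| b | Gap, 2b to 3b (× ULN) | ULN above which 300 U/L narrows it (U/L) | ULN from which 300 U/L closes it (U/L) |
|---|---|---|---|
| 1.1 | 2.2 to 3.3 | 90.9 | 136.4 |
| 1.2 | 2.4 to 3.6 | 83.3 | 125 |
| 1.4 | 2.8 to 4.2 | 71.4 | 107.1 |
| 1.5 | 3.0 to 4.5 | 66.7 | 100 |

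The documents give no ULN. For an assumed ULN of 30 to 60 U/L, the top of the widest gap is 4.5 × 30 = 135 to 4.5 × 60 = 270 U/L, so the 300 U/L limit does not bind.

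**Case 1 (ALT).** Baseline ALT is 1.4 × ULN. Later ALT is 4.0 × ULN (4.0/1.4 = 2.86 × baseline) and TBL 2.5 × ULN, with AST below 3 × its own baseline.
- Table 16-3, first row: excluded by the baseline.
- Table 16-3, second row: not met, since 2.86 < 3, unless the ALT ULN exceeds 300/4.0 = 75 U/L.
- Table 16-4: met, since 4.0 > 2 × 1.4 = 2.8.

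**Case 2 (AST).** Baseline AST is 1.4 and ALT 0.9 × ULN. Later AST is 4.0 (2.86 × baseline), ALT 2.5 (2.5/0.9 = 2.78 × baseline), TBL 2.5 and ALP 1.2 × ULN, with normal INR and no symptoms.
- Table 16-3, first row: excluded by the baseline AST.
- Table 16-3, second row: not met for an AST ULN up to 75 U/L.
- Table 16-4: not met, because ALT must exceed 3 × ULN.
- Table 16-5, TBL rows: not met, because the TBL rise is not isolated.
- Table 16-5, liver-AE row: could apply if the investigator judges the result to be such an AE.
- SAP Table 5-11: counted as potential Hy's Law.

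**Case 3 (TBL only).** Baseline TBL is 1.3 × ULN without Gilbert syndrome, and ALT and AST are normal. Later ALT is 6 and TBL 2.5 × ULN. The first row of Table 16-3 requires normal TBL and the second requires abnormal ALT or AST, so neither row applies. Table 16-4 acts.

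**Case 4 (isolated TBL).** Baseline ALT is 1.2 × ULN without Gilbert syndrome, and later isolated TBL is 3.5 × ULN. Table 16-5 calls for interruption. The raised-baseline row of Table 16-3 has no TBL trigger.

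**The case against.** The strongest reply is that little follows in practice. Table 16-4 is itself presented as follow-up for triggers, Section 10.2.1 links to it, and Section 9.1.1 cites Appendix 2 as a whole. A site that reads Table 16-4 directly will act in Cases 1 and 3, at least as strictly as Section 10.2.1 asks; Table 16-5 covers Case 4. This stands, and it is why the point is minor.

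A reader might infer that nothing in the protocol responds to the raised-AST case. The documents do not support that. The last row of Table 16-5 has no baseline or enzyme condition, and Section 10.1.1 makes a clinically significant laboratory result an AE. Case 2 could well be handled that way. What is missing is a numeric rule, so the response depends on judgement.

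It can also be said that Table 16-4 is wider than Table 16-3 elsewhere: for normal baselines it lists isolated ALT above 3 × ULN, while Table 16-3 starts at 5 × ULN. That is correct, and a missing Table 16-3 trigger is not by itself a defect. But that tier only asks for retesting and leaves treatment unchanged. The combined and symptomatic lines carry the potential Hy's Law pattern and, as the table reads, share the interruption action.

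The jaundice, liver-AE and ALP lines also stand under the normal-baseline row as printed. No conflict with the follow-up tables is shown for them: Table 16-4 does not name jaundice, Table 16-5 covers liver AEs at any baseline, and no follow-up table has an ALP row for any baseline.

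**Conclusion.** The mismatch is real and limited. For raised baseline ALT, results between 2 and 3 × baseline with TBL > 2 × ULN, INR > 1.5 or symptoms are action cases without a declared laboratory trigger. For raised baseline AST with ALT below the Table 16-4 limits, no table sets a numeric combined threshold, although the SAP would count Case 2 as potential Hy's Law. A subject with only TBL raised at baseline falls outside both rows of Table 16-3.

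The consequence is inconsistent declaration and follow-up. The number of subjects affected cannot be derived from the documents. No efficacy result is touched. A reader might infer either that safety counts are distorted or that they are certainly untouched. Neither is secured: SAP Section 2.8.4 summarises liver-enzyme abnormalities by reference to Appendix 2, while Table 5-11 lists its own thresholds.

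The conclusion assumes that Table 16-3 has the two rows it appears to have, and that the ULN is low enough for 300 U/L not to close the gap. The SAP records that the study was terminated, so the correction now matters mainly where this appendix is reused.

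**What to change.** In Table 16-3:

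1. Split the rows on ALT and AST only, keeping the Gilbert exception, so that subjects with raised baseline TBL alone are covered.
2. For raised baseline ALT or AST, add the combined TBL/INR trigger and the symptom trigger at > 2 × baseline or > 300 U/L. Judge each enzyme by its own baseline; an enzyme normal at baseline stays at > 3 × ULN.
3. Carry the TBL > 3 × ULN trigger to the raised-baseline row, to match Table 16-5.

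In Table 16-4, add AST to the combined and symptomatic lines on the same terms.

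Leave the isolated-ALT tiers and the jaundice, liver-AE and ALP lines as they are.

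With these changes Cases 1 to 4 all become declared triggers, and Case 2 gains a prescribed action. The cost is wording in one table and two lines of another. Some additional subjects, probably few, would receive liver follow-up, and the added AST cases would fall under the Table 16-4 interruption. Some of these subjects would have enzymes below 3 × ULN, from 2 × 1.1 = 2.2 × ULN at b = 1.1.
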